7.6. Prior and Concomitant Medications and Therapies

Medications and therapies that started and stopped prior to the first dose of AP01 are considered as prior medications. Medications and therapies that started prior to the first dose of AP01 and continued into the treatment period are considered as prior and concomitant medications. Medications or therapies with a start date from first dose of AP01 to 30 days after administration of the last dose of AP01 will be considered as concomitant medications.

Prior and concomitant medications will be coded according to World Health Organization (WHO) Drug Dictionary (March 2018 WHO DDE (Enhanced) B2 Format) for Concomitant Medication. The concomitant medications will be summarized for each treatment group and overall by Anatomical Therapeutic Chemical (ATC) level 2 (Therapeutic Main Group) and ATC level 4 (Chemical/Therapeutic Subgroup) using the number and percentage of patients. Medications will be sorted in descending order of frequency of ATC level 2 and ATC level 4 within ATC level 2 in the overall total column. A patient will be counted only once within each level of summation if the patient has taken a medication more than once.

All prior and concomitant medications and therapies will be listed.

This document is confidential.

SAP Version: 3.0 (15JUL2021)
Controlled Document ID: **3903A.01**, Effective Date 29-Oct-2018
Filing requirements: TMF

Page 29 of 52

Statistical Analysis PlanSponsor: Avalyn Pharma, Inc.; Protocol No.: AP01-002

8. Efficacy

The following efficacy analyses will be performed:

- Change from baseline in absolute FVC % predicted
- Change from baseline in cough frequency as measured by LCM
- Change from baseline in the total KBILD score and in KBILD breathlessness and activity domains
- Change from baseline in the total LCQ score.
- Change from baseline in cough severity as measured by VAS
- Change from baseline in extent of fibrosis and lung volumes as assessed by HRCT
- Change from baseline in D_{LCO}

The primary endpoint of interest for efficacy is the absolute change from Baseline to Week 24 in FVC % predicted. Linear mixed-effects models will be used to estimate slopes representing the mean change from Baseline to Week 24 in each treatment group, and the difference between treatment groups will be examined. Baseline FVC % predicted, region, age at screening, sex, baseline D_{LCO} % predicted, and baseline progression-related biomarker (CXCL13, CCL18, MMP3) values each categorized as >Median level vs. ≤Median level will be included as covariates in the model. Similar modeling strategies will be employed for longer-term data obtained from Part B of the study.

No control group is included in this study; however, there is ample data in the literature showing a consistent rate of decline in IPF patients not receiving anti-fibrotic therapies. Historical data from the placebo groups of the three Phase III clinical trials of oral pirfenidone (ASCEND and CAPACITY trials) showed an average decline in FVC % predicted of ~4% at 6 months. These results will be used as a historical comparator. For each AP01 treatment group, a one sample Wald test will test H_0 : mean change from Baseline to Week 24 in FVC % predicted $\leq -4\%$ vs H_1 : mean change from Baseline to Week 24 in FVC % predicted $> -4\%$. For each AP01 treatment group, a 95% one-sided confidence interval will be derived for the difference (between A01 and historical reference) in the mean change from Baseline to Week 24 in FVC % predicted. Additionally, we will compare the change from baseline in FVC % predicted at Week 24 for each treatment group to the average decline in FVC % predicted at 24 weeks for patients with no documented antifibrotic treatment calculated from a set of (1) Pulmonary Fibrosis Foundation (PFF) Registry patients and (2) Australian IPF Registry patients, with matching baseline characteristics. For each treatment group and each registry, a two-sided Wald test will test: H_0 : 24-week $FVC\ decline_{AP01\ group} = 24\text{-week}\ FVC\ decline_{registry}$ vs. H_1 : 24-week $FVC\ decline_{AP01\ group} \neq 24\text{-week}\ FVC\ decline_{registry}$. For each of the 2 AP01 treatment groups and for each of the 2 registries, a 95% two-sided confidence interval will be derived for the difference (between AP01 and registry) in the mean change from Baseline to Week 24 in FVC % predicted.

The primary population used for efficacy analyses will be the PP with the FAS used for specified sensitivity analyses.

This document is confidential.

SAP Version: 3.0 (15JUL2021)
Controlled Document ID: **3903A.01**, Effective Date 29-Oct-2018
Filing requirements: TMF

Page 30 of 52

Statistical Analysis PlanSponsor: Avalyn Pharma, Inc.; Protocol No.: AP01-002

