**Table 10: Probability of observing adverse events**

	Actual probability of event		
	1%	5%	10%
Chance of observing $\geq 1$ event	0.395	0.923	0.995

The Phase 3 study of oral pirfenidone in patients with IPF (ASCEND) showed a standard deviation (SD) of 4.5 based on the imputed mean change in % of predicted FVC at Week 26. Assuming a SD of 4.5, with 50 patients per arm, a two-sided 95% CI for mean change from baseline in % of predicted FVC will extend 1.25 from the observed mean. The ASCEND study showed a decrease of 1.5 and 3.9 in % of predicted FVC at Week 26 in the pirfenidone and placebo arms, respectively. Table 11 shows results of the ASCEND active and placebo arms and potential observed differences in the AP01-002 study, assuming a similar SD.

Because we have no prior data on efficacy outcomes with our compound, we are unable to make well informed predictions of effect size or variability. In lieu of that information, we have included some estimates of confidence intervals based on prior oral pirfenidone studies; however, we cannot be confident that our product will behave similarly and would not base hypothesis tests on this information. This study will give us an idea of which endpoints are most likely to be positively impacted by our product as well as solid estimates of both effect size and variability. In addition, if the effect is due to AUC or multiple peaks/day in the ELF rather than peak levels, based on our modeling from the BAL cohort in the AP01-001 study, we have around 75% power to show a difference between arms. With this sample size we can be confident on selecting dosing regimen(s) for future trials.

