All relevant patient data will be included in listings. All patients entered into the database will be included in patient data listings.

Pulmonary function tests (PFTs) (including D_{LCO}) are performed at each study visit.

The following PFTs will be performed at all visits (including Screening) using spirometry (and documented on the PFT eCRF form):

- FVC Liters (L)
- FEV₁ Liters (L)
- % Predicated FVC
- % Predicted FEV₁.

Pre-dose and post-dose spirometry will be performed at the Baseline visit.

At every visit, D_{LCO} ($\text{mL}/\text{min}^{-1}/\text{mmHg}^{-1}$) and % Predicted D_{LCO} will be obtained using the site's standard methodology.

FEV₁/FVC ratio will be derived as: $100 \times \text{FEV}_1/\text{FVC}$.

For comparisons to baseline, data from Visit 2 prior to the first dose of study drug will be used as baseline, unless otherwise noted. For PFTs, the pre-dose result will be used as baseline. Subgroup analyses will be performed based on baseline groupings for FVC, region, age, sex, D_{LCO} and progression-related biomarkers (CXCL13, CCL18, MMP3).

If either regimen is eliminated based on Part A outcomes, patients may be switched to the selected regimen for the remainder of their participation. Data summaries will be created to mimic this switch by using the following treatment grouping for Part B: (1) randomized to 100 mg twice daily; (2) randomized to 50 mg once daily and stayed on 50 mg once daily; (3) randomized to 50 mg once daily and switched to 100 mg twice daily; (4) randomized to 50 mg once daily total [groups 2 and 3 combined]; (5) overall total for Part B data. Descriptive within-patient analyses will be included for those patients who switch from 50 mg once daily to 100 mg twice daily. These analyses will include spider plots of change from baseline showing when the dose switch took place. Data listings will include a variable to denote the regimen switch and flag the time of the switch for affected patients.

No formal hypothesis tests are planned.

This document is confidential.

SAP Version: 3.0 (15JUL2021)
Controlled Document ID: **3903A.01**, Effective Date 29-Oct-2018
Filing requirements: TMF

Page 22 of 52

Statistical Analysis PlanSponsor: Avalyn Pharma, Inc.; Protocol No.: AP01-002

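### Each AP01 arm is tested at Week 24 against a fixed, rounded -4% from about 6 months with no sampling error, so the interval is too narrow and the nominal 5% is not assured

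*SAP*

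**What the plan says.** SAP Section 8 (Efficacy) notes that the study has no control group and turns to the placebo arms of ASCEND and the two CAPACITY trials, which "showed an average decline in FVC % predicted of ~4% at 6 months. These results will be used as a historical comparator". For each AP01 arm it specifies a one-sample Wald test of a mean Week 24 change of -4% or worse against a change better than -4%. In addition, "a 95% one-sided confidence interval will be derived for the difference" between AP01 and the historical value. It gives the reference no standard error, pooling method, exact week or data-handling rule. No alpha is stated; 5% one-sided is implied by the interval.

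The only detailed placebo figures near that time point are for ASCEND. Protocol 11.1 says that this "study showed a decrease of 1.5 and 3.9 in % of predicted FVC at Week 26 in the pirfenidone and placebo arms", respectively. Protocol Table 11 and SAP Table 2 add SD 5.2, n = 262 and a 95% interval of -4.53 to -3.27 for placebo. Protocol 11.1 describes the ASCEND SD of 4.5 as "based on the imputed mean change in % of predicted FVC at Week 26".

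On the AP01 side, the primary efficacy set is per protocol (SAP 8). The slope model needs baseline plus at least three post-baseline values, and imputation is confined to sensitivity analyses (SAP 6.3 and 8.1).

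SAP 6.1 says "No formal hypothesis tests are planned", as do Protocol 11.2.1 and 11.2.2. Protocol 11.5.1 calls the registry and historical comparisons exploratory. Section 8 also plans two-sided comparisons at 24 weeks with untreated patients from two registries, matched on baseline characteristics.

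**The concern.** An approximate average is used as if it were known exactly and measured at the same week as the AP01 endpoint. Three things follow.

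- **Variance.** An interval for a difference that carries the variance of one side only is too narrow.
- **Level.** If untreated decline at Week 24 is smaller than 4 points, an inert drug beats the null more often than 5% of the time. The ASCEND figure is already below 4 in size, and it is for Week 26.
- **Comparability.** The AP01 estimate is unimputed and per protocol. Protocol 5.6 lets a patient with excessive FVC decline be withdrawn in Part A, and Protocol 5.3 discontinues those who need oral pirfenidone or nintedanib. Early decliners can therefore leave the AP01 estimate, while the ASCEND figure is described as imputed.

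At stake is how far a statement that an arm declined less than untreated patients can be trusted, and whether it will be read as a formal test result when the plan says there are none.

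**Working it through.** **Inputs.** AP01 arm: SD 4.5, n = 50 (Protocol 11.1, SAP 3.5). ASCEND placebo: -3.9 at Week 26, SD 5.2, n = 262 (Protocol Table 11, SAP Table 2). CAPACITY placebo arms: -12.4 at 72 weeks and -6.9 at 48 weeks (Protocol 1.2.2). SD 5.2 is also tried for the AP01 arm, because under no drug effect the placebo SD is the natural choice.

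**Assumptions.** One-sided 5%, linear decline, 50 analysed per arm, and SE = SD/√n. The SAP does not say which estimate and SE the Wald test uses; a model-based SE would differ somewhat.

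**Reproducing the plan's figures.** Half-width for one arm: 1.96 × 4.5/√50 = 1.25. ASCEND placebo interval: -3.9 ± 1.96 × 5.2/√262 = (-4.53, -3.27). Both agree with the documents.

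**Standard errors.** AP01: 4.5/√50 = 0.636, or 5.2/√50 = 0.735. ASCEND placebo: 5.2/√262 = 0.321. Combined: √(0.636² + 0.321²) = 0.713, or √(0.735² + 0.321²) = 0.802. The ratios to the AP01 SE alone are 1.12 and 1.09.

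**Scaling to Week 24.** ASCEND: -3.9 × 24/26 = -3.60. CAPACITY 2: -12.4 × 24/72 = -4.13. CAPACITY 1: -6.9 × 24/48 = -3.45. Unweighted mean: -3.73.

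**Rejection rate with no drug effect.** For an untreated Week 24 mean μ, the rate is 1 − Φ((−4 + 1.645·SE − μ)/T). T = SE if the reference is treated as known; T is the combined SE if the reference error is counted.

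Example at μ = -3.60, SD 4.5: the numerator is -4 + 1.645 × 0.636 + 3.60 = 0.647. Then 0.647/0.636 = 1.017 gives 15.5%, and 0.647/0.713 = 0.907 gives 18.2%.

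| Untreated change at Week 24 | Known, SD 4.5 | Known, SD 5.2 | With SE 0.32, SD 4.5 | With SE 0.32, SD 5.2 |
|---|---|---|---|---|
| -4.00 (as the SAP assumes) | 5.0% | 5.0% | 7.1% | 6.6% |
| -3.90 (ASCEND, not scaled) | 6.8% | 6.6% | 9.2% | 8.3% |
| -3.60 (ASCEND, scaled) | 15.5% | 13.5% | 18.2% | 15.6% |
| -4.13 (CAPACITY 2, scaled) | 3.2% | 3.4% | – | – |
| -3.45 (CAPACITY 1, scaled) | 21.7% | 18.5% | – | – |
| -3.73 (mean of the three) | 11.2% | 10.1% | 13.9% | 12.1% |

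The documents give no SD or n for the CAPACITY placebo arms, so those two rows stop at the known-reference case and the last row borrows the ASCEND SE. With 40 analysed per arm, the scaled ASCEND row becomes 12.3-13.9% (known) and 14.0-16.2% (with reference error).

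On the ASCEND figure, most of the excess comes from the two-week gap: rounding alone gives 6.6-6.8%, and rounding plus scaling gives 13.5-15.5%.

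**The case against.** The strongest reply is that this is an exploratory comparison in an open-label Phase 1b study whose primary objective is safety. Protocol 11.5.1 announces historical and registry comparisons as exploratory and leaves the detail to the SAP, so making the comparison is not an undeclared change. That stands. It limits the severity and leaves only the test wording in conflict.

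Second, the SAP averages three trials, not ASCEND alone. One of them, scaled linearly, gives -4.13 and makes the test conservative. The exact week behind the CAPACITY contribution is not given, and scaling from 48 and 72 weeks is an assumption of this check. This stands too, and is why the result is a range. A pooled three-trial reference might have a smaller sampling error than ASCEND alone, but between-trial differences would add to it; the documents allow neither to be computed.

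Third, the SAP does address missing data. Its sensitivity analyses score FVC after death at 30% predicted and impute other early terminations, and the FAS is a supportive set. A reader might infer that deaths are simply left out, which is too strong: a patient who dies after three post-baseline visits still enters the slope model. What remains is that the SAP does not say the historical comparison is repeated on those analyses.

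None of this supplies the missing standard error or aligns the time points.

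**Conclusion.** The point holds as a should-fix. The one-sided interval is too narrow because it omits the reference's variance, and the nominal 5% is not assured. The size depends on the true untreated decline at Week 24: about 7% from ignored reference error alone, about 13-18% on the scaled ASCEND figure, and about 3-22% across the three trials with the reference treated as known. At their mean it is about 10-14%, depending on the SD and on whether reference error is counted. All of this rests on linear decline and 50 analysed per arm. The effect of comparing an unimputed per-protocol estimate with an imputed one cannot be computed from the documents.

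Four stronger readings are tempting but not supported:

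- **That the test rejects 15-18% of the time.** This needs ASCEND as sole benchmark, linear scaling, SD 4.5 and 50 analysed.
- **That every mismatch favours AP01.** Sampling error has no direction, the CAPACITY 2 figure goes the other way, and imputation is documented for ASCEND only.
- **That this is the only evidence against no treatment.** The matched-registry comparisons at 24 weeks are also planned.
- **That the six Wald tests (two historical, four registry) carry 1 − 0.95⁶ = 26% family-wise error.** The three tests on an arm share the same AP01 data, so independence fails.

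**What to change.** In SAP Section 8:

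1. Set in advance a Week 24 placebo reference, or match the time points, and state its source, pooling method, SE and data-handling rule.
2. Replace the one-sample test with a contrast of the AP01 arm mean and the reference, using Var(AP01 mean) + Var(reference).
3. Repeat the contrast on the FAS with the SAP's existing imputation for deaths and early terminations.
4. Report two-sided 95% intervals labelled exploratory, and delete the H0/H1 wording so that Section 8 agrees with SAP 6.1 and Protocol 11.5.1.

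The cost is SAP wording; no new trial data are collected. With the ASCEND SE, the interval is about 9-12% wider at the same confidence level (ratios 1.09 and 1.12). The contrast shrinks by about 0.3 points if the reference is -3.73 (4 − 3.73 = 0.27) or 0.4 points if it is -3.60. The pooled Week 24 figures must come from the source trials, because the documents do not give them.

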8.1. Primary Efficacy Endpoint and Analysis

Spirometry will be conducted at approximately the same time each visit (within 60 minutes of Day 1 spirometry measurement) with the patient in seated position. The test will be performed to American Thoracic Society/European Respiratory Society (ATS/ERS) guidelines³. On days of clinic visits (including the screening visit), patients must refrain from strenuous activity at least 12 hours prior to pulmonary function testing (PFT). FVC % predicted will be calculated using the ERS Global Lung Function Initiative 2012 equations² as outlined in the clinical study manual.

PFTs will be collected at Screening, Baseline and at each post-Baseline time point (Week 4, 8, 12, 16, 20, 24, 36, 48, 60, 72 and Follow-Up) as described in Section 6.1.

The primary efficacy endpoint is the change from baseline in absolute FVC % predicted from Baseline to Week 24. The population used for efficacy analyses of the primary variable will be the PP with the FAS used for the first sensitivity analyses.

A linear mixed-effects model (PROC MIXED) will be used and differences between treatment groups between slopes estimating the change from baseline in absolute FVC % predicted from Baseline to Week 24 will be examined. Baseline FVC % predicted, region, age at screening, sex, baseline DL_{CO} % predicted, and baseline progression-related biomarker (CXCL13, CCL18, MMP3) values each categorized as >Median level vs. ≤Median level will be included as covariates in the model. This analysis requires at least three post-baseline FVC % predicted values in addition to baseline be available for a patient to be included in the analysis so that the slope estimated is identifiable. Similar modeling strategies will be employed for longer-term data obtained from Part B of the study. Spirometry data collected after patients switched dosing regimen from 50 mg once daily to 100 mg twice daily will be omitted for this analysis.

For the sensitivity analyses of the primary efficacy endpoint, two different imputation strategies will be used to address missing in-clinic spirometry data used in the calculation of the change in absolute FVC % predicted from Baseline to Week 24. In both imputation strategies, missing data for early terminations other than deaths will be imputed for all visits following termination by assuming the average change at each visit calculated for all patients on the same cohort with FVC % predicted data available at that visit. For patients with missing data due to death, the remaining FVC % predicted values will be imputed as 30%.

For the second imputation strategy, in addition to imputing missing data due to early termination, home spirometry data will be used to replace missing in-clinic data using the following algorithm:

- Flag any biologically implausible home spirometry records for exclusion from analysis defined to be PFT measurements where the corresponding FVC % predicted value is <10 or >136.
- If home spirometry is available within the first two weeks following first dose of study drug, use it to calculate changes from baseline for home spirometry data.
- If home spirometry is not available within the first two weeks following first dose of study drug, use the patient's home spirometry data to fit a linear regression and the estimated intercept as a baseline for home spirometry data.

This document is confidential.

Statistical Analysis PlanSponsor: Avalyn Pharma, Inc.; Protocol No.: AP01-002

- Calculate all changes from baseline possible for a patient based on home spirometry data.
- Using any home spirometry data collected within the mapping window for a scheduled visit, create a pseudo office observation as the average of these home spirometry changes from baseline.
- Insert pseudo office observations for missed visits, setting the weeks of the observation to be the target weeks for that visit.

The primary variable will also be summarized by treatment group with descriptive statistics for the following subgroups: FVC (FVC % predicted ≤ 65 , $65 < \text{FVC \% predicted} < 80$, and FVC % predicted ≥ 80 at Baseline); region (Asia-Pacific and Europe); age at screening ($>$ Median level vs. \leq Median level); sex (Male and Female); baseline DLCO % predicted ($>$ Median level vs. \leq Median level) and baseline progression-related biomarkers (CXCL13, CCL18, MMP3) each categorized as $>$ Median level vs. \leq Median level.

The following statistics for in-clinic FVC and FVC % Predicted will be calculated and summarized by treatment group and displayed in a table:

- Summary statistics of in-clinic FVC and FVC % Predicted at Baseline and at each post-Baseline time point (Week 4, 8, 12, 16, 20, 24, 36, 48, 60, 72 and Follow-Up)
- Summary statistics of in-clinic FVC and FVC % Predicted reflecting the absolute change from Baseline to each post-Baseline time point (Week 4, 8, 12, 16, 20, 24, 36, 48, 60, 72 and Follow-Up).

The following plot will be produced for in-clinic FVC and FVC % Predicted:

- Mean FVC (or FVC % Predicted) Change from Baseline (\pm SD) vs. Visit Week (Week 4, Week 8, Week 12, etc.) with lines for each treatment group.

Linear mixed-effects models (PROC MIXED) will be used for the analyses. The model will include the change from baseline in in-clinic FVC (or FVC % Predicted) (measured at any time in the study) as the dependent variable and will include patient and time (continuous) as random effects, fixed effect of time and time-varying effects for treatment group and treatment-by-time interaction to account for those patients who switched dosing regimens from 50 mg once daily to 100 mg twice daily in Part B. Longitudinal plots at selected timepoints displaying the model adjusted, least square means and 95% confidence intervals will be produced.

All in-clinic pulmonary function data will be presented in a listing.

8.2. Secondary Efficacy Endpoint(s) and Analyses**8.2.1. Change from baseline in cough frequency as measured by LCM**

The LCM⁴ is an audio-based cough detection device that allows sounds to be reconstructed and measured as cough events. Patients that pass all of the screening criteria and will be randomized in the study will be provided with a cough monitor to wear for a 24-hour period prior to coming in for their Baseline visit. This will be used as their baseline reading. The LCM and mailing materials will also be dispensed at Visits 5 and 8. Patients will wear for a 24-hour period, fill out the cough monitor paper diary

This document is confidential.

SAP Version: 3.0 (15JUL2021)
Controlled Document ID: **3903A.01**, Effective Date 29-Oct-2018
Filing requirements: TMF

Page 32 of 52

Statistical Analysis PlanSponsor: Avalyn Pharma, Inc.; Protocol No.: AP01-002

and when complete, mail the LCM and diary back using the mailing materials provided. Further details regarding LCM dispensation and return will be outlined in the clinical study manual.

The following statistics for cough frequency (coughs/hour) as measured by LCM will be calculated and summarized separately for 24 hours and for awake time by treatment group and displayed in a table:

- Summary statistics of the cough frequency (coughs/hour) as measured by LCM at Baseline and at Visits 5 and 8 (Week 12 and 24)
- Summary statistics of the cough frequency (coughs/hour) as measured by LCM reflecting the absolute change from Baseline to Visit 5 and 8 (Week 12 and 24).

The following plot will be produced for cough frequency (coughs/hour) as measured by LCM:

- Mean Cough Frequency (coughs/hour) as measured by LCM Change from Baseline (\pm SD) vs. Visit Week (Week 12, Week 24) with lines for each treatment group.

A linear mixed-effect model (PROC MIXED) will be used and differences between treatment groups between the change from Baseline in coughs/hour as measured by LCM to Weeks 12 and 24 will be examined. Baseline cough frequency (coughs/hour), region, age at screening, sex, baseline D_{LCO} % predicted, and baseline progression-related biomarker (CXCL13, CCL18, MMP3) values each categorized as >Median level vs. \leq Median level will be included as covariates in the model. The model will include a random effect for patient and fixed effects for treatment, visit (Week 12 or Week 24), and the interaction between treatment and visit. To account for correlated repeated measures within patients a compound symmetric variance-covariance matrix will be used.

In order to assess the impact of treatment on cough in those patients for whom coughing is of greatest concern, additional analyses of cough frequency will be performed on the subset of patients with baseline cough severity VAS \geq 40 millimeters and in patients with baseline cough frequency \geq 10 awake time coughs/hour. When examining these subgroups, the outcome will be % change from baseline.

All data for LCM will be presented in a listing.

8.2.2. Change from baseline in the total KBILD score and in the KBILD breathlessness and activity domain score

The KBILD Questionnaire⁸ is a disease specific questionnaire consisting of 15 items that measures three specific domains: breathlessness and activities (questions 1, 4, 11 and 13), psychological (questions 3, 5, 6, 8, 10, 12 and 14) and chest symptoms (questions 2, 7 and 9). All items are scored on a seven-point response scale (1, 2, 3, 4, 5, 6, 7). The KBILD domain and total score ranges are 0–100; 100 represents the best health status. A KBILD total score can be derived from the 3 domain scores with the addition of question #15. The algorithm for scoring the KBILD Questionnaire is logit-based and described in Sinha et al. 2019⁹.

The KBILD Questionnaire will be completed at Baseline, all subsequent visits and the Follow-up visit. This is a paper-based questionnaire that will be completed by the patient at the relevant visits. The results of the KBILD will be entered into the appropriate eCRF. Appendix Section 14.2 presents the KBILD Questionnaire.

This document is confidential.

SAP Version: 3.0 (15JUL2021)
Controlled Document ID: **3903A.01**, Effective Date 29-Oct-2018
Filing requirements: TMF

Page 33 of 52

Statistical Analysis PlanSponsor: Avalyn Pharma, Inc.; Protocol No.: AP01-002

The following statistics for each KBILD questionnaire data domain and total score will be calculated and summarized by treatment group and displayed in a table:

- Number and percentage of patients in each treatment group that completed each survey at Baseline and at each post-Baseline time point.
- Summary statistics of the total KBILD score and each KBILD domain score at Baseline and at each post-Baseline time point (Week 4, 8, 12, 16, 20, 24, 36, 48, 60, 72 and Follow-Up)
- Summary statistics of the total KBILD score and each KBILD domain score reflecting the absolute change from Baseline to each post-Baseline time point (Week 4, 8, 12, 16, 20, 24, 36, 48, 60, 72 and Follow-Up).

The following plot will be produced for each KBILD domain score and the KBILD total score:

- Mean KBILD domain (or Total) score Change from Baseline (\pm SD) vs. Visit Week (Week 4, 8, 12, 16, 20, 24, 36, 48, 60, 72 and Follow-Up) with lines for each treatment group.

All KBILD Questionnaire data will be presented in a listing.

8.2.3. Change from baseline in the total LCQ score.

The LCQ Questionnaire¹⁰ is a disease specific questionnaire consisting of 19 items that measures three specific domains: physical (questions 1, 2, 3, 9, 10, 11, 14 and 15), psychological (questions 4, 5, 6, 12, 13, 16 and 17) and social (questions 7, 8, 18 and 19). All items are scored on a seven-point response scale (1, 2, 3, 4, 5, 6, 7). Domain scores are calculated as the total score from items in the domain divided by the number of items in the domain (range 1–7). The total score is the addition of all domain scores (range 3–21). For all domains, the higher the score the better the quality of life (QOL). If there are missing items, domain scores can be prorated by averaging the number of items actually answered. When there are missing data, prorating by domain in this way is acceptable as long as at least 50% of the items were answered (e.g., a minimum of 2 of 4 items).

The LCQ will be completed at Baseline, all subsequent visits and the Follow-up visit. This is a paper-based questionnaire that will be completed by the patient at the relevant visits. The results of the LCQ will be entered into the appropriate eCRF. Appendix 14.3 presents the LCQ.

The following statistics for each LCQ questionnaire domain and total score will be calculated and summarized by treatment group and presented in a table:

- Number and percentage of patients in each treatment group that completed each survey at Baseline and at each post-Baseline time point.
- Summary statistics of the total LCQ score and each LCQ domain score at Baseline and at each post-Baseline time point (Week 4, 8, 12, 16, 20, 24, 36, 48, 60, 72 and Follow-Up)
- Summary statistics of the total LCQ score and each LCQ domain scores reflecting the absolute change from Baseline to each post-Baseline time point (Week 4, 8, 12, 16, 20, 24, 36, 48, 60, 72 and Follow-Up).

The following plot will be produced for each LCQ domain score and the LCQ total score:

This document is confidential.

SAP Version: 3.0 (15JUL2021)
Controlled Document ID: **3903A.01**, Effective Date 29-Oct-2018
Filing requirements: TMF

Page 34 of 52

Statistical Analysis PlanSponsor: Avalyn Pharma, Inc.; Protocol No.: AP01-002

- Mean LCQ domain (or total) score Change from Baseline (\pm SD) vs. Visit Week (Week 4, 8, 12, 16, 20, 24, 36, 48, 60, 72 and Follow-Up) with lines for each treatment group.

All LCQ Questionnaire data will be presented in a listing.

